13.1.3 Statistical Analysis Plan

The primary and some secondary analyses will include all eligible and treated patients. Exceptions to this include: analysis of toxicity data, which will include all patients who received study drug regardless of eligibility.

Time-to-event data, such as PFS and OS, will be estimated using the Kaplan-Meier method, and Cox proportional hazards models will be used to estimate hazard ratios. Comparisons of groups will be made using the logrank test and Cox modeling.

Categorical data, such as response rates (CR+PR) and toxicity, will be compared using Fisher's exact tests with a one-sided type I error rate of 10%; multivariable logistic regression modeling will be used to adjust for the effect of any covariates that are associated with these categorical outcomes. Though none are currently planned, any continuous outcomes will be analyzed using Wilcoxon rank sum test, and multivariable linear regression models may be used to adjust for multiple associations with outcome.

Modeling procedures will implement backward selection; variables significant at the 0.10 level in the univariate setting will be chosen for inclusion in an initial full model, and at each step the least significant variable will be removed from the model. Only those covariates with $p < 0.05$ will remain in any final models, unless there are factors identified by the study team as crucial to model interpretation.

Point estimates of all endpoints will be accompanied by the corresponding two-sided 80% confidence intervals. The method of Atkinson and Brown will be used for the estimation of the confidence interval for response.

In the event that there are missing data, no imputation of the missing data will be conducted. We will assume that data are missing at random and will conduct all analyses as originally planned because we do not anticipate an excess of missing data.

Subset analyses of all variables, including correlatives, are considered to be exploratory in nature.

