13.1.4 Correlative Analysis

The correlative studies planned for this trial include evaluation of flow cytometry, RNA seq, and cytokine release data with outcomes on this trial. Biopsies are planned pre-treatment, 4 weeks post initiation of therapy, and at the time of disease progression.

For the flow cytometric immunoprofiling on both tumor and immune cells, t-distributed neighbor embedding (t-SNE) analyses will be performed, resulting in the identification of "hot" and

“cold” clusters as previously described^{5,6}. Each of the immunologic markers/parameters will be analyzed individually and in compilation to form such clusters. We hypothesize that outcomes may vary according to the value of such markers and/or hot/cold cluster status.

With respect to the single-cell RNA sequencing analyses, we hope to determine whether or not single cell expression profiles can distinguish malignant and non-malignant cell types, and whether or not bulk tumors can segregate to distinct clusters on the basis of their inferred cell type composition. We hope to evaluate the association of profile and/or cluster type with outcomes.

Lastly, the cytokine release studies will study 15-20 different cytokines and their relationship with patient outcomes, with the overarching hypothesis that change in cytokines over time will be associated with outcome to therapy with immune checkpoint inhibition.

We may employ a variety of statistical techniques for the analyses of these data. The rate of change at a particular time point such as 4 weeks may be compared to baseline measures and will be analyzed for association with patient demographics and/or disease characteristics using the Kruskal Wallis test. Presence or absence of mutations in plasma will be analyzed for association with other variables using Fisher’s exact test. To account for the repeated measures over time, we may potentially use these data as time varying covariates in multivariable Cox models to study their impact on outcomes like PFS and OS.

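### Section 13.1.3 selects covariates by p-value and states no correction for it, so kept marker effects are biased away from the null and the reported 80% intervals, taken together, do not cover 80%

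*Combined protocol and SAP*

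**What the plan says.** Section 13.1.3 sets one rule for model building, a backward procedure that starts from a univariate screen: "variables significant at the 0.10 level in the univariate setting will be chosen for inclusion in an initial full model". Terms are then dropped one at a time, weakest first. A second threshold decides where this ends: "Only those covariates with $p < 0.05$ will remain in any final models". The one exception is for factors that the study team regards as essential for reading the model. Cox models are to supply hazard ratios, and logistic models are to adjust categorical outcomes such as response.

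On precision, the same section says "Point estimates of all endpoints will be accompanied by the corresponding two-sided 80% confidence intervals". It names a specific technique for one endpoint only: "The method of Atkinson and Brown will be used for the estimation of the confidence interval for response". No interval method is named for odds or hazard ratios, and nothing is said about shrinkage, bootstrap, cross-validation or external validation of a selected model.

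Section 13.1.4 indicates how many candidates there may be: "the cytokine release studies will study 15-20 different cytokines and their relationship with patient outcomes", besides flow-cytometry markers and RNA profiles. It expects 64 of 80 patients to have analyzable results and gives one planning effect for a marker: 25% vs 60% in two groups of 32. Section 13.1.3 labels subset analyses, correlatives among them, as exploratory. Section 1.3 makes correlates of response and resistance secondary objectives.

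**The concern.** A marker reaches the final model only if its estimate in these patients was large enough to pass both thresholds. The reported effect is therefore drawn from the upper part of its sampling distribution, even when the marker is real, and an ordinary interval is centred on that value. Null markers that pass by chance sit in the same model, and the reader cannot tell them from real ones.

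The plan gives the response rate its own named interval method and leaves the selected effects without one. At stake is how far the odds or hazard ratios of the correlates, and their error bars, can be taken at face value. Limiting the number of false discoveries would remove some of the problem, but a real marker that is kept would still be overstated.

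**Working it through.** **Inputs from the documents.** Screen at 0.10, retention at p<0.05, two-sided 80% interval (13.1.3). 64 analyzable patients, 32 vs 32, 25% vs 60%, stated power 91%, 15-20 cytokines (13.1.4). First stage of 43 patients (13.1.2).

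**Assumptions.** Two-sided Wald p-values (sidedness is not stated). Independent binary markers split 50:50, one of them real. Logistic model for response, with all candidates offered to one model. Hazard ratios were not simulated: the direction is the same, the size was not computed.

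**1. The plan's own figure.** Exact enumeration of the one-sided 0.10 Fisher test, 32 vs 32, 25% vs 60%, gives power 0.910. The stated 91% reproduces.

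**2. The planning effect on the model scale.** Odds ratio = (0.60/0.40)/(0.25/0.75) = 4.5; log 1.504. Standard error = √(1/8 + 1/24 + 1/19.2 + 1/12.8) = 0.545. Expected z: δ = 1.504/0.545 = 2.76, about 79% power at two-sided 0.05.

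**3. Null markers.** Retention needs |z| > 1.96, while an 80% interval reaches only 1.28 standard errors either side. Every kept marker's interval therefore excludes the null, and a kept null marker has 0% coverage by construction.

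**4. A real marker, normal approximation.** Given z > 1.96, the overstatement of the log odds ratio is [δ + φ(1.96−δ)/Φ(δ−1.96)]/δ, and conditional coverage is [0.90 − Φ(1.96−δ)]/Φ(δ−1.96).
- δ = 2.76: (2.76 + 0.290/0.788)/2.76 = 1.13; coverage (0.90 − 0.212)/0.788 = 87%.
- δ = 1.96 (50% power): (1.96 + 0.399/0.5)/1.96 = 1.41; coverage 0.40/0.50 = 80%.
- δ = 1.43 (30% power): (1.43 + 0.347/0.298)/1.43 = 1.81; coverage (0.90 − 0.702)/0.298, about 67%.

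Exact enumeration of all 32-vs-32 tables at the planning effect gives 1.15-fold and 88%.

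**5. The full rule**, simulated with 5 or 20 candidates, 1,500 trials each, 64 patients:

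| True OR | Log-OR overstatement, real kept marker (5 / 20) | Coverage, real kept marker (5 / 20) | Null markers kept per model (5 / 20) |
|---|---|---|---|
| 4.5 (planning) | 1.17 / 1.24 | 88% / 83% | 0.16 / 0.82 |
| 3.0 | 1.38 / 1.49 | 83% / 78% | 0.18 / 0.93 |
| 2.5 | 1.60 / 1.73 | 76% / 68% | 0.22 / 0.91 |
| 2.0 | 2.07 / 2.20 | 56% / 50% | 0.19 / 0.99 |
| 1.5 | 3.00 / 3.42 | 22% / 3% | 0.22 / 0.99 |

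With 15-20 standardised continuous markers, three of them real, odds ratios of 1.5 and 2.0 per SD give median inflation of 1.9-2.0 and 1.4.

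**6. All kept markers together, planning effect.** With 20 candidates the real marker is kept in 0.814 of trials with coverage 0.826, and 0.82 null markers are kept with coverage 0: 0.814 × 0.826/(0.814 + 0.82) = 0.672/1.634 = 41%. Over 15-20 candidates the simulations give about 39-46%. With 5 candidates the same sum is 0.812 × 0.88/(0.812 + 0.16) = 74%.

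**7. On the odds-ratio scale.** A 1.15 to 1.25-fold overstatement of log 4.5 means a typical reported odds ratio of 4.5^1.15 = 5.6 to 4.5^1.25 = 6.6. For a true odds ratio of 2.0, 2^2.07 to 2^2.20 is 4.2 to 4.6.

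**8. Stop after stage 1.** 0.80 × 43 = 34 analyzable. δ falls to 2.76/√(64/34) = 2.01, about 50% power. The planning-effect marker is then overstated about 1.4-fold by the formula and about 1.6-fold (median) under the full rule.

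**9. Without selection.** If every marker's univariable interval is reported, exact enumeration gives 78-82% coverage for true odds ratios from 1 to 4.5; simulation gives 76-80%.

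**The case against.** The strongest reply has four parts.

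- **The interval sentence speaks of endpoints.** Section 13.1.1 lists these as response, PFS, OS, duration of response and toxicity. Applying the sentence to marker effects is an inference. That stands. But if it does not apply, the plan states no interval for the odds and hazard ratios it sets out to estimate, and the wording still needs a decision.
- **Nothing says that 15-20 cytokines enter one model.** Section 13.1.4 gives the correlatives other methods as well and says that immunologic markers will be analyzed individually. That stands too: the pooled figure of 39-46% rests on this assumption, and with 5 candidates it is about 74%. Individual analysis does not commit the plan to reporting every estimate, selected or not.
- **The correlatives are exploratory.** This limits what may be claimed. It does not remove the bias or restore coverage, and correlates of response and resistance are the study's stated purpose in Section 1.1.
- **Much of the coverage shortfall is false discovery.** Correct for the pooled figure. The inflation of real effects is separate.

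A reader might infer that real markers will be overstated 1.4 to 2-fold as a property of the plan. The documents do not support this: it needs a true binary odds ratio of about 2 to 3 (or 1.5 to 2.0 per SD), and no such effect is stated. Nor do they support the inference that a real marker's own interval under-covers at the planning effect; it covers at or slightly above 80%. The plan also promises no AUC or C-index, so optimism in discrimination is a fault only if one is reported.

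**Conclusion.** The point holds, with its size tied to the assumed effect. Section 13.1.3 selects on p-values and corrects for nothing, so kept effects are biased away from the null and the set of reported intervals falls short of 80% coverage.

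- **Planning effect (OR 4.5, 64 patients):** log odds ratio of a real kept marker overstated about 1.15 to 1.25-fold, own coverage about 81-88%. With 15-20 candidates, about 0.6-0.9 null markers kept per model and coverage over all kept markers about 39-46%.
- **Assumed weaker effects (binary OR about 2 to 3, or 1.5 to 2.0 per SD):** about 1.4 to 2-fold.
- **Stop after stage 1, OR 4.5:** about 1.6-fold.

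These are log-scale figures under two-sided tests and independent markers offered to one logistic model. A reader might extend the point to the trial's main result. That would be wrong: the response-rate decision does not use this selection. This is an inexpensive improvement to an exploratory, secondary biomarker objective.

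**What to change.** In Section 13.1.3:

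1. List the candidate markers in advance. Report the univariable odds or hazard ratio with its 80% interval for every one of them, selected or not, as the main effect estimate.
2. For any multivariable model built by selection, repeat the whole procedure (screen and backward steps) in bootstrap resamples. Report selection frequencies and optimism-corrected, shrunken estimates, and label the naive final-model intervals as not adjusted for selection. If a discrimination measure is reported, give its optimism-corrected value.
3. State whether the 80% interval sentence covers odds and hazard ratios.

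Penalised regression on the pre-listed markers is an alternative to item 2, not a requirement. The univariable estimates are not adjusted for other markers, and the bootstrap shrinks estimates without guaranteeing 80% coverage, which is why the label is needed.

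The cost is SAP wording and a little more analysis work, with no added patients or samples. Reported marker effects will be smaller.

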13.1.4 Correlative Analysis

The correlative studies planned for this trial include evaluation of flow cytometry, RNA seq, and cytokine release data with outcomes on this trial. Biopsies are planned pre-treatment, 4 weeks post initiation of therapy, and at the time of disease progression.

For the flow cytometric immunoprofiling on both tumor and immune cells, t-distributed neighbor embedding (t-SNE) analyses will be performed, resulting in the identification of "hot" and

“cold” clusters as previously described^{5,6}. Each of the immunologic markers/parameters will be analyzed individually and in compilation to form such clusters. We hypothesize that outcomes may vary according to the value of such markers and/or hot/cold cluster status.

With respect to the single-cell RNA sequencing analyses, we hope to determine whether or not single cell expression profiles can distinguish malignant and non-malignant cell types, and whether or not bulk tumors can segregate to distinct clusters on the basis of their inferred cell type composition. We hope to evaluate the association of profile and/or cluster type with outcomes.

Lastly, the cytokine release studies will study 15-20 different cytokines and their relationship with patient outcomes, with the overarching hypothesis that change in cytokines over time will be associated with outcome to therapy with immune checkpoint inhibition.

We may employ a variety of statistical techniques for the analyses of these data. The rate of change at a particular time point such as 4 weeks may be compared to baseline measures and will be analyzed for association with patient demographics and/or disease characteristics using the Kruskal Wallis test. Presence or absence of mutations in plasma will be analyzed for association with other variables using Fisher’s exact test. To account for the repeated measures over time, we may potentially use these data as time varying covariates in multivariable Cox models to study their impact on outcomes like PFS and OS.

With a given sample size of 80 patients in this study, we expect that at least 80% of patients (n=64) will yield analyzable laboratory results for a given endpoint. For a given marker or abnormality occurring at a rate of 50%, the marker can then be used to define two patient cohorts with n=32 patients in each group. This sample size provides 91% power to detect differences in the rate of another binary variable (such as progression, response, or presence of a resistance mutation) with frequencies of 25% and 60%, respectively, while testing with a one-sided 0.10-level Fisher’s exact test.

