1.3 Secondary Objectives

- Evaluate immunologic correlates of response and primary resistance to ipilimumab and nivolumab therapy in NSCLC.
- Evaluate immunologic correlates of acquired resistance to ipilimumab and nivolumab in NSCLC, with acquired resistance defined as participants who experience an objective radiologic response or stable disease per RECIST 1.1 criteria followed by disease progression.
- Assess the progression-free survival (PFS) rate, duration of response (DoR), and overall survival (OS) of the combination utilizing RECIST 1.1 criteria.

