9.2 Collection of Fresh Tumor Tissue

Fresh tumor tissue biopsies will be obtained from patients enrolling to the trial at the following times:

- Baseline - any time following signing of the informed consent form but prior to cycle 1 day 1
- On-treatment - between cycle 1 day 22 and cycle 1 day 36
- Optionally at the time of disease progression per RECIST 1.1 criteria - time of progression biopsies should be obtained prior to the initiation of another cancer treatment. In the event that it is not possible to perform the biopsy before another treatment is begun, biopsies can be obtained up to 30 days after the date at which disease progression was determined.

The pre-treatment biopsy is mandatory for all participants for enrollment to the trial. The on-treatment biopsy is mandatory unless it would pose a significant medical risk to the participant as judged by the treating investigator and clinician performing the procedure. Time of progression biopsy is optional for participants when clinically feasible. Additionally, if clinically feasible participants may undergo fluid collection procedures (e.g. pleural effusion drainage) **in addition** to tumor tissue biopsy collection. If the participant undergoes a surgical resection for standard of

care needs at any point during the trial, the resected tissue may also be collected for analysis as clinically appropriate. Please refer to the laboratory manual for specific collection and handling guidelines.

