13.1.2 Sample Size Considerations

The primary comparison will include all eligible and treated patients, of whom 80 will be accrued. Whereas traditional chemotherapy confers a response rate (CR + PR) of roughly 30%, the goal of this trial is to target a response rate of 44%, which will be taken as evidence of activity of combination therapy with ipilimumab and nivolumab. We will employ a Simon two stage design for this trial. In the first stage, a total of 43 eligible and treated patients will be enrolled. Accrual will proceed to the second stage if at least 15 patients achieve a CR or PR among those first 43 patients. In the second stage, an additional 37 patients will be enrolled. If at least 29 responses are observed among all 80 patients enrolled, then the combination of ipilimumab and nivolumab will be deemed worthy of additional study. This trial has 88% power against the null hypothesis while testing at the one-sided level of 0.109, and the probability that the study stops early under the null is 0.71.

We note that per RECIST 1.1, these responses must be confirmed with a second scan after the

initial response is determined. We also note that patients who are deemed unevaluable for response will not be replaced, and will be included as non-responders in the assessment of the best objective response rate.

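### The 64 analysable patients and 91% power in section 13.1.4 cannot be reached for analyses that need tissue at acquired resistance

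*Combined protocol and SAP*

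**What the plan says.** Section 13.1.4 sizes the correlative work once, for any laboratory endpoint. From 80 patients, it expects that "at least 80% of patients (n=64) will yield analyzable laboratory results for a given endpoint". With a marker present in half of them, "the marker can then be used to define two patient cohorts with n=32 patients in each group". The plan then states 91% power to separate rates of 25% and 60% in a second binary variable, "while testing with a one-sided 0.10-level" Fisher's exact test. Its examples of that second variable are progression, response and a resistance mutation.

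Other sections define a narrower population and sampling scheme for one objective:

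- Section 1.3 makes immunologic correlates of acquired resistance a secondary objective, with "acquired resistance defined as participants who experience an objective radiologic response or stable disease per RECIST 1.1 criteria followed by disease progression". A separate bullet there covers response and primary resistance.
- Section 9.2 requires the pre-treatment biopsy, and requires the on-treatment biopsy unless it carries significant medical risk. By contrast, "Time of progression biopsy is optional for participants when clinically feasible". Footnote I of the study calendar (Table 16) also calls the progression biopsy optional.
- Section 9.2.4 accepts that some biopsies will yield too little tissue, and applies tissue exome sequencing only to pre-treatment and progression samples.
- Section 13.1.2 allows the trial to end after 43 patients: "the probability that the study stops early under the null is 0.71".

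No section gives an expected number of progression biopsies or a separate power figure for them.

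**The concern.** A single sample size is offered for every correlative endpoint, but one of the two resistance objectives draws on a subset of a subset. A patient contributes progression tissue at acquired resistance only after gaining disease control, then progressing, then agreeing to a biopsy that is feasible and yields usable material. Because section 13.1.4 is the only correlative power statement and mentions resistance mutations, its 91% can be carried over to that analysis. A null result from perhaps a few dozen progression samples could then be read as a well-powered negative. The stake is the interpretation of one secondary objective; the primary response-rate test is not affected.

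**Working it through.** **Inputs from the documents.** N = 80, stage 1 of 43, continue with at least 15 responses, null 30%, target 44% (13.1.2). Laboratory yield 80%, marker prevalence 50%, rates 25% v 60%, one-sided 0.10 Fisher's exact test (13.1.4).

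**Inputs not in the documents.** The share with response or stable disease (d), the share of those who later progress (g), and progression-biopsy uptake (u). Values used below are assumptions.

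**1. The plan's own figure.** 80 × 0.80 = 64, and 64 × 0.50 = 32 per group. Power is the sum, over all pairs (x1, x2) whose one-sided Fisher p-value is at most 0.10, of Bin(x1; 32, 0.25) × Bin(x2; 32, 0.60). The result is 0.9103, so the stated 91% reproduces.

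**2. What 64 progression-tissue samples would need.** Expected samples = 80 × d × g × u × 0.80 = 64 × d × g × u. Setting this to 64 gives d × g × u = 1: every patient gains disease control, progresses and is biopsied. No patient would then have primary resistance, which section 1.3 also plans to study. Even at 100% laboratory yield, d × g × u would have to be 64/80 = 0.80. This step uses no outside rate.

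**3. Size of the shortfall under assumed rates.** Same test, same 25% v 60%, equal groups:

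| Assumption | Samples | Per group | Power |
|---|---|---|---|
| d 0.60, g 0.70, u 0.30: 80 × 0.60 × 0.70 × 0.30 × 0.80 | 8 | 4 | about 0.21 |
| d × g 0.50, u 0.50: 80 × 0.50 × 0.50 × 0.80 | 16 | 8 | 0.38 |
| intermediate | 24 | 12 | 0.52 |
| d 0.80, g 0.90, u 0.70: 80 × 0.80 × 0.90 × 0.70 × 0.80 | 32 | 16 | 0.67 |
| d × g 0.75, u 0.70: 80 × 0.75 × 0.70 × 0.80 | 34 | 17 | 0.71 |
| d 0.80, all progress, all biopsied: 80 × 0.80 × 0.80 | 51 | 25 | 0.84 |

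The last row is very favourable and still falls short of 0.91. Exact Fisher power is saw-toothed (30 per group gives 0.917, above the value at 32), so small differences in n should not be over-read.

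**4. Blood confined to the acquired-resistance subset.** Biopsy uptake drops out: 80 × d × g × 0.80. With d 0.60 and g 0.70 this is 27; with d 0.80 and g 0.90 it is 46. Both are below 64, because only part of the trial population qualifies.

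**5. Stage 1 stop.** 43 × 0.80 = 34.4, so about 34 samples and 17 per group, with power 0.71 even for baseline markers. The chance of stopping is P(X ≤ 14 of 43): 0.708 at a 30% response rate, matching the plan's 0.71, and 0.086 at 44%. The stopping probability of 0.71 and the power of 0.71 are different quantities that happen to agree.

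**The case against.** The strongest reply is that section 13.1.4 contains no error. Its arithmetic is right, it does not name acquired resistance, and it states its premise of 80 patients. A resistance mutation need not come from a progression biopsy: exome sequencing is planned on archival or pre-treatment tissue (9.1, 9.2.1), and 13.1.4 also mentions mutations in plasma. Section 13.1.3 calls subset analyses, including correlatives, exploratory. The sizes in the table rest on rates the documents do not supply, and progression tissue might be compared with the same patient's earlier biopsy instead of being split by a marker present in half the patients.

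Most of this stands, and it rules out a stronger reading. A reader might infer that acquired resistance as a whole can be studied only through optional biopsies and so can never use 64 patients. The documents do not support that. Plasma is scheduled on day 1 of each cycle and off treatment (9.3), and blood mononuclear cells at baseline, Cycle 2 Day 1 and off treatment (9.4), neither labelled optional. Acquired resistance is also a clinical outcome, so a baseline or on-treatment marker can be tested against it across all patients. Nor is the stage 1 stop a defect in itself: any two-stage design has less correlative data if it stops, and at the target rate stopping is unlikely.

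What the reply does not answer is step 2. The statement is worded for any endpoint, nothing exempts progression tissue, and the design cannot supply 64 such samples. Exploratory status supports a descriptive label; it does not support an unqualified 91%.

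**Conclusion.** The concern holds for analyses that need tissue at acquired resistance. For these the stated 64 and 91% are not attainable under the plan's own definition, sampling rules and 80% yield. That conclusion requires only that some patients have primary resistance, do not progress, or are not biopsied. The size is uncertain: across the assumed rates, 8 to 34 samples give power of about 0.21 to 0.71 for the same comparison, and a very favourable case gives 51 samples and 0.84. Blood analyses restricted to the acquired-resistance subset are also smaller than 64, for the separate reason that not all patients qualify. For baseline and on-treatment tissue or blood markers across all patients, 64 and 91% remain plausible with full enrolment.

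**What to change.** Amend section 13.1.4 as follows:

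- Limit the 64 and 91% to markers measured at baseline or on treatment, in tissue or blood, across all patients with all 80 enrolled.
- State the expected number of progression-tissue samples as an explicit assumption, with power over a range for 25% v 60%: 0.38, 0.52, 0.71 and 0.84 at 8, 12, 17 and 25 per group. Add that blood analyses confined to the acquired-resistance subset will also have fewer than 64 patients.
- Label analyses of progression tissue as descriptive.
- Note that a stage 1 stop leaves about 34 analysable patients (17 per group) and about 0.71 power, with stopping probability 0.71 at a 30% response rate and 0.09 at 44%.

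The cost is wording. No patients are added and the primary test does not change. The drawback is a less favourable stated power for one secondary objective.
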